For this cluster randomized trial, we assume a Type I error rate of 0.05 and a desired power of 0.8 for the primary outcomes. Our study will include 60 microclusters (30 intervention, 30 control) with at least 8 participants in each cluster (n=480 across all clusters). We will have no fewer than 480 and can enroll up to 720. The number of participants enrolled will depend on our dynamic enrollment strategy that we've discussed already. We assume an intraclass correlation (ICC) of 0.05. For our primary outcomes (and all survey-based outcomes), we will fit a marginal model using generalized estimating equations (GEE) to estimate the effect of the intervention relative to control. Under these assumptions, we will be able to detect an intervention effect of 0.33 s.d at 80% power with 30microclusters per arm (60 total) and 8 participants per microcluster.⁹ This is a conservative estimate of power since we will adjust for the baseline value of the outcome and other covariates associated with the outcome. If we are only able to sample from 50 microclusters (25 per arm; n=400 across all clusters), we will be able to detect a moderate effect size of 0.37 s.d. at 80% power. Assuming up to 25% attrition between baseline and endline, we would still be able to detect a treatment effect of 0.31 s.d.

Statistical Analysis

Individual-level primary and secondary outcomes

For all primary and secondary outcomes drawn from our two-wave survey of 720 trial participants, we will assess differences in outcomes between the intervention and comparison groups using Generalized Estimating Equation models (GEE) that account for clustering at the study microcluster level. We will use canonical link functions for all outcomes. All models will adjust for the baseline level of the outcome, all microcluster-level characteristics used in the covariate constrained randomization (see randomization protocol),¹⁰ any individual characteristics found to be imbalanced between the intervention and control groups at baseline.

We will conduct an intention-to-treat analysis: participants that move out of (or across) study clusters, separately engage with community partner services while in the control group, or do not engage with these services while in the treatment group will all be considered exposed to their original treatment assignment.

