Given that our study includes two primary outcomes, we will address for simultaneous inference using a stacked GEE approach.¹¹ This approach adequately covers family-wise Type I errors in a manner that is more efficient than overly conservative approaches such as Bonferroni-Holm.

We will use a similar set of approaches for the survey-based secondary outcomes. For these outcomes we will report both unadjusted p-values as well as p-values adjusted for multiple inference (again based on models using a stacked GEE approach).

Will conduct four sensitivity analyses. First, we will assess for non-random attrition by regressing a binary indicator for each participant equal to 1 if the participant did not complete a follow-up survey on the treatment indicator, microcluster level attributes used in the covariate constrained randomization procedure, and any individual-level covariates that were not balanced at baseline (adjusting standard errors for clustering at the microcluster level). In the event of non-random attrition (denoted by a statistically significant coefficient on the treatment indicator from the above regression), we will use inverse probability weighing approaches (IPW) to address potential biases. We will also use an alternate strategy that calculates the lower bound of treatment effects by assigning the "best" (i.e., most positive) sample value of an outcome to attritors in the control group and "worst" sample value of an outcome to attritors in the treatment group.¹²

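### Inverse probability weighting runs only if arm significantly predicts dropout; that test cannot see arm-specific selection and often misses unequal dropout rates, so the weighted analysis should be unconditional

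*Combined protocol and SAP*

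**What the plan says.** Section 9 (Analysis plan), Statistical Analysis, lists four sensitivity analyses. The first regresses an indicator of a missing follow-up survey on arm, the microcluster covariates used in the randomization, and any individual covariates found unbalanced at baseline. Attrition counts as non-random when this test is positive, "denoted by a statistically significant coefficient on the treatment indicator from the above regression", and weighting is used in that event. No significance level is given for the test. The regression names neither the baseline outcome nor any interaction with arm. No imputation or other model is planned for participants without a follow-up survey.

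The next sentence adds a worst-case analysis: "We will also use an alternate strategy that calculates the lower bound of treatment effects". Control dropouts receive the best value in the sample and intervention dropouts the worst. The text does not settle whether this is always done or only after a positive test.

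Two other statements matter. The main GEE models adjust for the baseline value of the outcome. The Power Calculations allow for substantial loss over 24 months: "Assuming up to 25% attrition between baseline and endline".

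**The concern.** A completer analysis is biased when the people lost differ between arms in ways that relate to the outcome and that the model does not remove. That can happen with identical dropout rates. It is plausible here: intervention participants receive a cash grant, counselling and help with appointments, while controls receive only a contact list at the end of the intervention period. A test of the arm coefficient does not address this. Even for what it does test, a non-significant result at this sample size is weak evidence that dropout rates are equal. Following the rule as written, the team could leave out the weighted analysis when it is needed, for both primary outcomes.

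**Working it through.** **Inputs from section 9.** 30 microclusters per arm; 480 to 720 participants, so 480/60 = 8 to 720/60 = 12 per cluster; attrition up to 25%; Kessler-6 range 0-24. On clustering the plan says "We assume an intraclass correlation (ICC) of 0.05", which refers to outcomes.

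**Assumed.** Two-sided 0.05 for the gate; dropout ICC from 0 to 0.05.

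**1. The plan's detectable effect, used only as a yardstick.** Design effect 1 + 7 × 0.05 = 1.35. Standard error √(2 × 1.35/240) = 0.106. Detectable effect (2.002 + 0.848) × 0.106 = 0.302 SD with 58 df. The stated 0.33 SD is not reproduced; that is a separate matter and does not affect this point.

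**2. Power of the gate.** SE = √{[p₁(1−p₁) + p₂(1−p₂)] × DE/n}, with DE = 1 + (m−1) × ICC and n per arm; power comes from the noncentral t with 58 df. For 20% against 30%, the bracket is 0.16 + 0.21 = 0.37.

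| Per cluster | Dropout ICC | SE | 0.10/SE | Power |
|---|---|---|---|---|
| 8 | 0.05 | √(0.37 × 1.35/240) = 0.0456 | 2.19 | 58% |
| 8 | 0 | √(0.37/240) = 0.0393 | 2.55 | 71% |
| 12 | 0.05 | √(0.37 × 1.55/360) = 0.0399 | 2.51 | 69% |
| 12 | 0 | √(0.37/360) = 0.0321 | 3.12 | 87% |

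For 22% against 28%, power over the same four settings is 25-45%. A 15-point gap (17.5% against 32.5%) is caught at least 90% of the time.

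**3. What the gate cannot see.** Simulation: 2,000 trials per setting, 60 clusters of 8, ICC 0.05, true effect zero, 25% dropout in each arm, no baseline adjustment. Dropout was correlated with the outcome in opposite directions in the two arms.

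| Correlation | Completer bias (SD) | Gate fires |
|---|---|---|
| 0.1 | 0.08 | 5.6% |
| 0.2 | 0.17 | 5.5% |
| 0.3 | 0.26 | 4.8% |

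With selection in the same direction in both arms, bias is about zero and the gate again fires about 5% of the time. The gate cannot tell the two situations apart, and a larger sample does not change that. These biases are for an unadjusted comparison, so they show what the gate misses, not the bias to expect under the plan.

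**4. Size under the planned baseline-adjusted model.** Suppose 25% drop out in each arm and the log-odds of dropout change by +0.7 per SD of a second baseline variable x in one arm and −0.7 in the other.
- The completers' means of x then differ by about 2 × 0.7 × 0.17/0.75 = 0.32 SD, where 0.17 is the average of p(1−p).
- After adjustment for the baseline outcome, the bias is about 0.32 × (r_xy − r_xb × r_by). Here r_xy is the correlation of x with the endline outcome, r_xb that of x with the baseline outcome, and r_by that of baseline with endline.
- With r_by = 0.5 and r_xb = 0.3 (assumed): r_xy = 0.3 gives 0.32 × 0.15 = 0.05 SD, and r_xy = 0.5 gives 0.32 × 0.35 = 0.11 SD.
- Simulation of the adjusted model gives about 0.04-0.11 SD. Letting r_xb run from 0.5 to 0.2 widens the formula's range: 0.32 × (0.3 − 0.25) = 0.02 to 0.32 × (0.5 − 0.10) = 0.13 SD.
- If x is the baseline outcome itself, then r_xb = 1 and r_xy = r_by, and the bias is zero.
- Weighting with arm interactions brings the bias to about zero, with the SD of the estimate at 0.103-0.109 with or without weights.

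**5. The worst-case bound on Kessler-6.** With 25% missing per arm and completers spanning 0-24, the imputed difference is 0.75 × (completer difference) + 0.25 × (24 − 0). The added term is 6 points, or 1.0-1.5 SD if the SD is 6 to 4 points (assumed). This is a ceiling, because the plan uses sample extremes, which may be narrower. The planned effect of 0.33 SD would be 1.3-2.0 points on the same SDs.

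**The case against.** The best defence is that the plan has other protection.

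- **The bound.** A reader might infer that complete-case results would stand unchallenged. The documents do not support that: the lower bound follows the weighting sentence without an explicit condition of its own, and if always run it is a harsh test. What remains is that it is one-sided, so bias against the intervention is never examined; its trigger is unclear; and at 25% loss it would overturn almost any effect of the planned size, so it cannot separate modest bias from none.
- **Baseline adjustment.** A reader might take a bias of about 0.10 SD from an unadjusted comparison (0.32 × 0.3). The planned models adjust for the baseline outcome, which removes the bias if dropout depends on that alone and reduces it otherwise. This stands, and the size given here is for the adjusted model.
- **Missed rate gaps may be harmless.** With the same selection in both arms (normal model, correlation 0.2), 20% against 30% dropout biases the result by only about 0.03 SD. This also stands. It shows that the arm coefficient is a poor guide in both directions: a significant one need not mean bias.
- **Weighting is not a cure.** It cannot repair dropout driven by unmeasured health at follow-up, and its success in the example depends on the dropout predictor having been measured.
- **Meaning of 'best'.** One could read the plan's gloss on 'best' as the numerically highest value, which on Kessler-6 is the most distressed and would reverse the bound. Favourable is the more natural sense. This is an ambiguity to clear up, not a shown error.

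**Conclusion.** The concern holds in this form: the decision to weight rests on a test of the wrong condition, and that test has limited power at the minimum sample. At equal dropout rates it fires about 5% of the time whatever the bias. For 20% against 30% dropout it fires 58-71% of the time at 8 per cluster and 69-87% at 12. In the illustrative case the planned model is biased by about 0.04-0.11 SD, which is 12% to 33% of the stated 0.33 SD detectable effect (0.04/0.33 to 0.11/0.33).

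The power figures rest on an assumed dropout ICC and an assumed two-sided 0.05. The bias rests on constructed opposite selection and assumed correlations, for which the documents give no values; it shows what is possible, not what is expected. Nothing in the documents shows that attrition will be biased, or that the complete-case estimate would be the only one reported. The lower bound is a partial check and does not replace weighting.

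**What to change.** - Run the inverse-probability-weighted analysis in all cases, as a pre-specified sensitivity analysis for both primary outcomes. Put in the dropout model the baseline outcome, other baseline predictors already collected (for example demographics and the financial measures), and their interactions with arm. At 480 enrolled and 25% loss there are 0.25 × 480 = 120 non-completers, so name a short list of predictors in advance.
- Keep the attrition regression as description only, with no decision attached to its p-value.
- State that the bound is always run, report it in both directions, and define 'best' for each outcome as the most favourable value (the lowest for Kessler-6).
- Say in the plan that weighting does not address dropout that depends on unmeasured follow-up health.

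The cost is plan wording and a few extra models on data already being collected. The weighted intervals may be slightly wider, although the loss of precision in the simulated example was negligible.

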Neighborhood microclusters (hereafter, microcluster) served as the intervention unit for the study. To form these microclusters, a master list of every block, or street segment from one intersection to the next intersection, in the 75 eligible census tracts was created. A total of 8,462 blocks were included in the master list. A shapefile of selected blocks was imported into R. A random block was chosen as an index block and a 0.125 (one eighth) mile diameter buffer was created around that block. All other blocks that fell within this radius were used to form a microcluster of geographically proximal blocks. A block was included in the microcluster if at least half of the street segment fell within the microcluster boundaries. This microcluster formed a study area. All blocks that were included in the microcluster were removed from the master list to ensure no overlap of microclusters. Next, an additional 0.125-mile exclusion zone buffer was created on all sides of each microcluster. The purpose of the exclusion zone was to create an additional buffer between microclusters to minimize potential spillover effects from the interventions. This process was then repeated until 60 total non-overlapping microclusters were in each city section.

Our goal was to have a final set of microclusters that minimized overlap of microcluster exclusion zones to reduce potential spillover and contamination effects across trial arms. To do this in a random manner, the process to create 60 study microclusters with 0.125-miles exclusionary zones was repeated 1,000 times to create 1,000 unique maps. An analysis was run to determine the total area of exclusion zone buffer overlap for each of the 1,000 microcluster map iterations, which was then ordered from lowest to highest. We then selected the bottom microcluster iterations with the lowest exclusion zone overlap. From this list, one iteration was selected at random to determine final study sites.

Randomization

We randomly assigned the 60 microclusters to treatment (intervention, n=30 microclusters) and control (nonintervention, n=30 microclusters) groups. Prior to randomization, microclusters were stratified by city section (West and North). The land area and number of streets in each section was near-equal, allowing for stratification pre-constrained randomization.¹

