Within the city section strata, we conducted a covariate-constrained randomization process in order to ensure balance between microclusters randomized to intervention and those randomized to control based on relevant sociodemographic variables. Covariate-constrained randomization quantifies baseline imbalance of microcluster-level covariates (both categorical and continuous) across all microclusters using a balance metric and then randomly selects one randomization schema from those with acceptable balance. Furthermore, the intraclass correlation coefficient calculation – a measure of reliability – remains unaffected under a constrained randomization model.²

We chose the following covariates to balance on: age (categorized by shares under age 19, 19-49, 50-64, and 65 and above); gender; median income; unemployment rate; amount of vacancy; and tree canopy. We did not balance on race/ethnicity (e.g., % Black) or poverty rates, since initial criteria for study site selection focused on census tracts whose populations were at least 80% Black and with elevated poverty rates. The covariates were measured based on their distribution of means by each microcluster using block group data from the US Census Bureau's 2020 ACS. Each microcluster's mean is the weighted mean for the covariates based on percent of land area in each census block group in which the microcluster sits. A microcluster could be in one census block group or could cross over 2 or 3 census block groups. Following the literature, we used a threshold of 0.2 for standardized mean differences in the covariates.

We used the -cvcrand- package, specifically the -cvrall- function, in R to calculate the final covariate balance metric and selection schema at random after covariate balance by cluster was achieved.²

Enrollment

Participant recruitment will commence in September 2023 and will run through May 2023 (or until we enroll at least 480, but no more than 720, in the main trial). Recruitment in control and intervention microclusters will occur simultaneously. The data analyst who performed the randomization will randomize microcluster order (stratified by intervention and control status and city section) to determine the order in which recruitment occurs.

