Second, we will estimate models that additionally include binary indicators denoting any CC who conducted interviews and fostered linkages with financial partners for each participant. Third, we will estimate a permutation inference model in which we will run our GEE models without covariates in 1,000 permutations, each of which represents a model in which treatment assignment is randomly assigned (or shuffled) 1:1 at the microcluster level (95% CIs for this method, which does not assume a specific error structure, will be constructed a the interval of estimates ranging from the 2.55th to the 97.5th percentile of the distribution of 1,000 point estimates).¹³ We will compare estimates from our main models to estimates from these uncontrolled models. Differences would suggest potential unobserved confounding. In the event of substantive differences, we will estimate bounds on the ITT effects.¹⁴ Fourth in the event of prevalent (e.g., greater than 20%) non-adherence to the intervention, we will estimate average treatment on the treated (ATT) parameters to recover causal effects of full participation in the intervention on the outcomes.¹⁵ (Given that the place-based interventions will occur without direct involvement of trial participants, non-adherence in this case would most likely to apply to the financial interventions.)

Microcluster level secondary outcomes

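### The permutation analysis shuffles treatment freely across microclusters although the trial randomised within city section and only among balanced allocations, so its interval is not design-based and is conservative to the extent that those factors predict the outcome

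*Combined protocol and SAP*

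**What the plan says.** Section 8.2, Randomization, describes a restricted allocation of 60 microclusters, 30 to each arm. They were first divided by city section, and then: "Within the city section strata, we conducted a covariate-constrained randomization process". The procedure "randomly selects one randomization schema from those with acceptable balance". The balancing variables are "age (categorized by shares under age 19, 19-49, 50-64, and 65 and above); gender; median income; unemployment rate; amount of vacancy; and tree canopy", and the rule is that "we used a threshold of 0.2 for standardized mean differences in the covariates".

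Section 9, Statistical Analysis, gives the permutation analysis as the third of four sensitivity analyses. The plan is to "run our GEE models without covariates in 1,000 permutations", in each of which "treatment assignment is randomly assigned (or shuffled) 1:1 at the microcluster level". The 95% interval is the range of the shuffled estimates, "ranging from the 2.55th to the 97.5th percentile of the distribution of 1,000 point estimates". Its stated use is to set the main estimates beside these uncontrolled ones. Neither the section strata nor the balance rule is mentioned there, and no other part of the document restricts the shuffle.

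**The concern.** A permutation analysis is design-based only if it redraws allocations by the mechanism that was actually used. Here the design excluded unequal section splits and large covariate imbalances, and the shuffle brings both back. Because the permuted models contain no covariates, nothing in them absorbs that imbalance. The spread of the shuffled estimates can therefore include variation that the randomisation had already removed.

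What is at stake is the one interval that the plan describes as free of an assumed error structure. If it is wider than the design warrants, it can appear not to support an effect that the primary model finds.

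**Working it through.** **The plan's own figure.** The documents give no number for the permutation distribution. The nearest is the detectable effect of 0.33 SD (60 microclusters of 8, ICC 0.05, power 0.80). The standard error of the difference is sqrt(2 × [1 + 7 × 0.05] / 240) = 0.106. With two-sided alpha 0.05 and 58 degrees of freedom, the detectable effect is 0.302 SD (0.297 with normal quantiles), so 0.33 is not reproduced. It does appear with alpha 0.025 (0.334) or with 6 completers per cluster (0.336). Nothing below depends on it.

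**Inputs from the documents.** 60 microclusters, 30 per arm; at least 8 participants each; ICC 0.05; two sections; a 0.2 limit on standardised mean differences (SMD). The balancing variables give about 8 free columns: 3 independent age shares plus 5 others.

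**Assumptions.** 30 microclusters per section split 15:15; every |SMD| below 0.2, applied either overall or within each section; normal covariates with correlation 0 or 0.3; equal cluster sizes. R² is the share of between-cluster variance explained by section and covariates.

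**Step 1: how many free shuffles belong to the design?** The chance of a 15:15 split in both sections is C(30,15)² / C(60,30) = 0.203. In simulation, 0.17-0.27% of free shuffles also met the 0.2 limit overall on all 8 columns. That is about 2 of the planned 1,000.

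**Step 2: how much wider can the free reference distribution be?** The variance of a cluster mean is ICC + (1 − ICC)/m = 0.05 + 0.95/8 = 0.169, of which 0.05/0.169 = 29.6% is between clusters. If the design balanced the predictive factors perfectly, the width ratio (free over design) would be 1 / sqrt(1 − 0.296 × R²). If the band is used as a 5% test, its true size would then be 2 × [1 − Φ(1.96 × ratio)].

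**Step 3: simulation with the actual 0.2 limit.** The unadjusted difference in cluster means stands in for the covariate-free GEE. Width ratios come from 300 outcome sets per scenario. The size column spans these runs and a second, separate simulation, except at 90%, which comes from the first only. At R² 75%, section carries 10 points and the covariates 65.

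| R² | Ratio, perfect balance | Ratio, simulated | Size, perfect balance | Size, simulated |
|---|---|---|---|---|
| 0% | 1.000 | 1.00-1.01 | 5.0% | about 5% |
| 25% | 1.039 | 1.03-1.05 | 4.2% | 4.3-4.5% |
| 50% | 1.083 | 1.07-1.08 | 3.4% | 3.5-3.8% |
| 75% | 1.134 | 1.11-1.14 | 2.6% | 2.8-3.1% |
| 90% | 1.168 | 1.13-1.16 | 2.2% | 2.5-2.8% |

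In outcome units, the free half-width is 1.96 × 0.106 = 0.208 SD. At R² 50% the design's is about 0.208/1.083 = 0.192 SD. Used as a test at a true effect of 0.30 SD, the free shuffle loses about 2, 3 and 5 points of power at R² 25, 50 and 75%, and none at 0%.

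**Step 4: sensitivity to cluster size.** At R² 50% with 6 completers per cluster (25% attrition), the simulated size is 3.9%. With 12 per cluster (720 participants), the between-cluster share is 0.05/(0.05 + 0.95/12) = 0.387, and the perfect-balance ratio is 1 / sqrt(1 − 0.5 × 0.387) = 1.11.

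**The case against.** The strongest reply is that little depends on this. The analysis is one of four sensitivity analyses, the error is conservative, and no permutation p-value is planned. The estimate under the actual allocation is the same however the labels are shuffled; only the interval changes. Primary inference comes from the covariate-adjusted GEE with stacked multiplicity control. All of this stands, and it limits the weight of the point.

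Three stronger readings are tempting, and the documents do not support them.

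- **The interval is too wide whatever the data.** It is not: at R² = 0 the widths agree. The documents give no R². They do call the balancing variables relevant, adjust every main model for them, and expect adjustment covariates to be related to the outcome. Some excess is therefore plausible, but its size is unknown.
- **The primary p-values are undermined.** Nothing in the shuffle enters the primary models.
- **Leaving out covariates is itself a mistake.** Section 9 wants an uncontrolled comparator and says so. Replacing it with the adjusted model would remove the planned comparison.

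It could also be said that the shuffle may have been meant to respect the strata. The text does not say so, and where the plan stratifies another random step (recruitment order, in sections 6 and 8.2) it states it.

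**Conclusion.** The mismatch between the shuffle and the randomisation is clear from the text, and the interval as specified is not design-based. Its consequence is conditional and modest. With the plan's ICC of 0.05 and 8 per cluster, the interval ranges from no wider than it should be to about 14% too wide as R² goes from 0 to 75%. Even full explanation of the between-cluster variance could not push the ratio past 1 / sqrt(1 − 0.296) = 1.19 under perfect balance. In no scenario was the free interval materially narrower, so the error does not favour the intervention.

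The sizes rest on the assumed R², the 15:15 split per section, 8 balance columns, and the 0.2 limit holding for every covariate. Section 8.2 refers to both a balance metric and a threshold, without saying exactly how acceptance was decided. The mismatch itself rests on none of these.

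Correcting the 2.55th percentile, or the labelling of a null reference band as a confidence interval, would leave this problem in place; those are separate matters. The point is worth settling before analysis, but it does not threaten the primary result.

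**What to change.** In section 9, state that the 1,000 re-allocations are drawn only from those the randomisation could have produced: within West and North, with the actual numbers per arm in each section, and meeting the same balance criterion, regenerated from the same cvcrand inputs. State that criterion exactly. Keep the covariate-free GEE as the planned uncontrolled comparator.

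Optionally, add a second run over the same restricted set with the treatment estimate from the covariate-adjusted primary GEE as the test statistic, so that the permutation result also checks the primary analysis. Say whether city section is in that model: it is a stratum, not one of the listed balancing covariates.

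The cost is a sentence or two of plan text and a few lines of code, with no change to conduct or data collection. The documents do not say whether the accepted allocations were saved. If they must be regenerated, the simulated acceptance of 0.94-1.2% among stratified draws (limit applied overall) means roughly 1,000/0.012 = 83,000 to 1,000/0.0094 = 106,000 draws for 1,000 accepted allocations, which is a small computation. A limit applied within each section would need more draws. The number of GEE fits stays at 1,000 per outcome unless the optional run is added.

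### The 95% CI in the permutation sensitivity analysis is a no-effect reference range centred on zero, not a confidence interval for the treatment effect

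*Combined protocol and SAP*

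**What the plan says.** Section 9, Statistical Analysis, lists four sensitivity analyses for the individual-level outcomes. The third is a permutation analysis: "we will run our GEE models without covariates in 1,000 permutations", where in each one "treatment assignment is randomly assigned (or shuffled) 1:1 at the microcluster level". The interval is introduced as "95% CIs for this method, which does not assume a specific error structure", and the text adds that it "will be constructed a the interval of estimates ranging from the 2.55th to the 97.5th percentile of the distribution of 1,000 point estimates". The plan mentions no recentring on the observed estimate, no inversion of the test and no permutation p-value.

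The main-model estimates are then compared with those from the uncontrolled models, and the plan states: "Differences would suggest potential unobserved confounding". If the differences are substantive, bounds on the ITT effects follow.

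Two other passages bear on this. Section 8.2, Randomization, stratified the 60 microclusters by city section (West and North) and then constrained the allocation on covariates: "Following the literature, we used a threshold of 0.2 for standardized mean differences in the covariates". Section 9 says of the main models: "We will use canonical link functions for all outcomes".

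**The concern.** A confidence interval should contain the effect sizes compatible with the data. The percentiles of shuffled-label estimates show instead where the estimate would fall if treatment did nothing. The range can therefore show that an observed estimate is extreme under no effect, but it cannot say how large the effect is.

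If the range is printed as a 95% CI beside the estimate, it spans zero in every trial. When the effect is large it usually excludes the estimate it is meant to accompany. A reader would conclude that the sensitivity analysis fails to support the main result, even when the permutation test rejects no effect.

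There are two smaller points.

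- The shuffle is described as plain 1:1, with no mention of the city-section strata or the balance rule that governed the actual allocation.
- A gap between adjusted and unadjusted estimates is weak evidence of unobserved confounding in a randomised trial.

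**Working it through.** **Inputs.** From Section 9, Power Calculations: 30 clusters per arm, at least 8 participants each, ICC 0.05, design effect size 0.33 SD, 25% attrition. From Section 9, Statistical Analysis: 1,000 shuffles and the 2.55th to 97.5th percentiles, which nominally hold 97.5 - 2.55 = 94.95% of the distribution. The outcome has total SD 1 and an identity link.

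**The plan's figure.** The stated confidence level is 95%. It cannot be reproduced as coverage of the effect at any effect size examined.

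**Why the centre is zero.** With 30:30 shuffling, each assignment and its mirror image are equally likely and give estimates of opposite sign. The full permutation distribution is therefore symmetric about zero for any data. Using 1,000 draws adds only Monte Carlo error: the SD of the centre across simulated trials was 0.003 to 0.005.

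**Approximate width.** With m participants per cluster, the variance of a cluster mean is 0.05 + 0.95/m. For m = 8 it is 0.05 + 0.11875 = 0.16875. A true effect d adds 15d²/59 to the sample variance of the 60 cluster means. At d = 0.33 this is 15 × 0.1089/59 = 0.0277, giving a total of 0.1964. The permutation SD of the difference is sqrt(0.1964/15) = 0.114, so the range is about ±1.96 × 0.114 = ±0.22. A true effect widens the range but does not move it.

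**Simulation of the rule as written** (1,500 trials × 1,000 shuffles per setting; the 0.15, 0.50 and 1.0 SD rows come from a separate run of 2,000 trials each):

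| True effect (SD) | 6 per cluster (8 less 25%) | 8 per cluster | 12 per cluster |
|---|---|---|---|
| 0.15 | – | 99.8% | – |
| 0.20 | 93% | 71% | 23% |
| 0.25 | 31% | 6% | 0% |
| 0.33 | 0.1% | 0% | 0% |
| 0.50 | – | 0% | – |
| 1.0 | – | 0% | – |

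Entries are the share of trials in which the range contains the true effect. At 8 per cluster and 0.33 SD the mean range is -0.220 to +0.221. It contains zero in 100% of trials, and the observed estimate lies outside it in 87%. With unequal cluster sizes of 4 to 12 the mean range at 0.33 SD is -0.225 to +0.226, again with 0% coverage. Under no effect the estimate falls outside the range in 5.1% of trials, so the range is sound as a test.

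**Alternatives.** Test inversion gives a mean interval of 0.12 to 0.54 at 0.33 SD. Its coverage is 93.5% to 95.7% by setting and 94.8% over 12 settings (18,000 trials). Recentring the range on the observed estimate covers 96.6% at 0.33 SD and 99.6% at 1.0 SD, so it is conservative.

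**Plain versus constrained shuffle.** With balancing covariates assumed to be prognostic, one check gave null rejection of about 1.7% for the plain shuffle against 5.7% for the constrained one. The direction is conservative. The size depends on how prognostic the covariates are, which the documents do not state.

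**Adjusted versus unadjusted.** Take 480 participants, adjustment for the baseline outcome only, and no confounding. The difference between the two estimates then has SD of roughly r × sqrt(2 × 0.16875/30) = r × 0.106, where r is the baseline–endline correlation. For an assumed r of 0.4 to 0.7 the simulated SD is 0.043 to 0.075, and the difference exceeds 0.05 SD in 23% to 51% of trials (0.05 is an illustrative cut-off).

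For binary outcomes on the logit scale, a perfectly balanced covariate can also move the odds ratio. With 50% covariate prevalence, 40% control prevalence and a covariate odds ratio of 6 to 10 (all assumed), a conditional 0.60 becomes a marginal 0.65 to 0.68. With a covariate odds ratio of 2 to 3 it becomes only 0.61 to 0.62.

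**The case against.** The strongest case concerns weight. This is one parenthesis in one of four sensitivity analyses. No decision rule is attached to the interval, and as a reference band it holds its 5% level. The misleading report arises only if the range is printed as a CI; the plan cites a source for the method, and how the team would present it cannot be known. All of that stands and limits the severity. It does not repair the text, which calls the range a 95% CI and gives no other construction.

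Some of the figures also need careful reading.

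- The 87% is the power of the permutation test at 0.33 SD, not a separate defect. It exceeds 80% because the stated inputs at two-sided 0.05 give a detectable effect of (1.960 + 0.842) × sqrt(2 × 1.35/240) = 0.297 SD, not 0.33.
- For small effects the range over-covers rather than under-covers.
- Non-collapsibility cannot affect either primary outcome, since both are continuous with an identity link. Its size also depends on strong assumed covariates.
- The plan's confounding sentence is hedged, and bounds follow only from substantive differences.

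On the remedy, test inversion assumes a constant shift, which is an approximation for a bounded 0–24 Kessler-6 score. Its coverage was checked with equal clusters and a plain shuffle, not with the constrained one.

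The objection also exposes an ambiguity. The plan never names an unadjusted fit under the actual assignment. If the uncontrolled models are the shuffled fits, a real effect would differ from their zero-centred estimates and could be read as confounding.

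**Conclusion.** The concern holds. Followed as written, the third sensitivity analysis reports a range centred on zero under the label 95% CI. Its coverage of the true effect is near 100% for small effects and about 0% at 0.33 SD. The zero centring is exact by symmetry and depends on neither the ICC, the cluster size nor the power figure. The coverage percentages do depend on those inputs.

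The damage is confined to this sensitivity analysis and how it is reported; the main GEE inference is untouched. The unrestricted shuffle and the reading of adjusted–unadjusted differences are secondary, and their size rests on assumptions the documents do not settle. The change should be made, but it is not critical to the trial.

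**What to change.** Amend the third sensitivity analysis as follows.

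1. Report the unadjusted estimate under the actual assignment with a permutation p-value from the shuffle distribution. If the percentile range is shown, call it a null reference band. Correct 2.55th to 2.5th.
2. For continuous outcomes, obtain the 95% CI by test inversion: subtract a hypothesised effect from the intervention arm, re-permute, and keep the values not rejected at 5%. State the constant-shift assumption. Recentring on the observed estimate is simpler, but should be described as conservative.
3. For binary outcomes, report the permutation p-value only, or invert on the risk-difference scale. For ordinal outcomes, the p-value alone is enough.
4. Draw permutations within city section and from allocations that meet the same balance rule, regenerated from the randomisation program if they were not stored.
5. Say which fits the uncontrolled models are. Show adjusted and unadjusted estimates side by side, and remove the statement that a difference points to unobserved confounding. Whether to keep bounds for attrition or differential recruitment is a separate choice for the trial team.

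The cost is analysis-plan wording and modest computing, with no change to data collection or the main analysis.
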